1. ABSTRACT

The conceptual framework of the proposed trial is grounded in our prior experience in the conduct of dietitian-directed dietary interventions with the provisions of food. In this randomized controlled trial (RCT), the Diet-Gout trial or DIGO, we will randomize at least 40 adults with gout and with hyperuricemia (serum uric acid [SUA] ≥ 7 mg/dL) who are not actively taking urate-lowering drugs (ULDs) to a grocery intervention designed to reflect the previously published Dietary Approaches to Stop Hypertension (DASH) diet. This trial has been funded by the Rheumatology Research Foundation. Following a crossover design, all 40 adults will undergo 4 weeks of a self-directed feeding period (reference) and a DASH grocery intervention (value \$105 per week). The primary outcome is serum uric acid. Our approach is adapted from the framework of the recently completed “Five Plus Nuts and Beans Trial.” Groceries will be purchased from an online grocery store (AmazonFresh) in serving proportions that reflect the DASH diet – a diet high in fruits, vegetables, low-fat dairy and lean meats and low in fat and saturated fat. This, as a corollary, will reduce consumption of a pro-gout dietary pattern: an unhealthy dietary consumption pattern that is due in parts to excesses (e.g., red meat and sugary soda) and deficiencies (e.g., vegetable protein and low-fat dairy) in typical American diets.

2. SPECIFIC AIMS

Primary Aim

Aim 1. To determine the effect on the DASH Diet on uric acid among adults with self-reported gout and hyperuricemia. In this randomized controlled trial (RCT) of 40 patients with hyperuricemia (SUA level ≥ 7 mg/dL) or gout, who are not taking ULDS and have a uric acid ≥ 7 mg/dL, we will compare the effects of 4 weeks of DASH groceries compared to typical grocery purchases on SUA levels.

Hypothesis 1. The DASH diet will show a clinically meaningful improvement in lowering SUA levels as compared to the control diet.

Other aims: To estimate the effects of the DASH diet on the following outcomes:

- A. Clinic blood pressure
- B. Orthostatic hypotension
- C. Timed up and Go
- D. Body mass index
- E. Urinary sodium, potassium, and creatinine excretion
- F. Self-reported fruit, vegetable, and fat consumption
- G. Gout severity
- H. Global physical function
- I. Joint pain
- J. Fasted LDL cholesterol
- K. Fasting blood sugar
- L. Urine pH and uric acid level

3. BACKGROUND

Substantial and Increasing Disease Burden of Gout – The Modern Gout Epidemic.

Perpetuated by the “Western” lifestyle and resulting obesity epidemic, the prevalence of gout has increased over the past few decades to **3.9% of US adults (8.3 million individuals)**.¹ This prevalence increases with age to 9.3% of US adults over 60 years (4.7 million). The disease burden of gout has been similarly rising worldwide for decades.² **Compelling Lack of Dietary Intervention Trials in Gout.**

Despite substantial epidemiologic evidence for the potential extrapolation of certain dietary and lifestyle factors as therapeutic strategies in gout care, there are no dietary intervention trials for high-strength evidence, as clearly recognized by the latest ACR guidelines and the 2015

Agency for Healthcare Research and Quality (AHRQ) review for the American College of Physicians (ACP),³ constituting a critical gap in the field of gout care.

The Need for the Current Trial

As mentioned above, a compelling research gap exists in dietary intervention studies for gout. The current trial will be significant for the following reasons: (1) Halting or reducing the remarkable and rising disease burden of gout (an excruciatingly painful arthropathy) has important public health implications; (2) Reducing both gout risk and simultaneously the major cardiovascular-metabolic comorbidities and sequelae associated with hyperuricemia and gout, which could lead to improved survival; (3) The DASH diet is particularly appealing, as 74% of US gout patients have hypertension,⁴ which contributes to the rising prevalence of gout in the US; (4) Other key elements of effective anti-gout lifestyle approaches have reasonable palatability, sustainability, and practical simplicity (for patients and practitioners alike), which are not provided by the current low purine diet approach. To these effects, our proposal to evaluate the potential anti-gout effects of a well-established, sustainable dietary approach is highly promising; and (5) Ultimately, the approach that lowers SUA levels among gout patients with proven added cardiovascular-metabolic benefits would have a significant positive impact among millions of gout patients in the US and beyond.

Urate-Lowering Effect of the DASH Diet in Hyperuricemic Non-Gouty Individuals

Our recent ancillary analysis (N = 103) of an original DASH diet trial has found that the DASH diet lowers SUA levels as compared to a typical American diet (i.e., control diet), particularly among those with hyperuricemia (i.e., by 0.8 mg/dL in those with a baseline SUA level of 6-7 mg/dL, and by 1.3 mg/dL in those with a baseline SUA \geq 7 mg/dL).⁵ While this trial did not specifically target a gout population, these findings suggest that the DASH diet could have considerable urate-lowering benefits among those with hyperuricemia or gout.

[figure not shown]
All DASH trials (published in *NEJM* and *JAMA*)^{6,7} found that the DASH diet substantially reduced both systolic and diastolic blood pressure among hypertensive as well as normotensive adults. For example, the original DASH trial found that among subjects with hypertension, the DASH diet reduced systolic and diastolic blood pressure by 11.4 and 5.5 mmHg more, respectively, than the control diet.

DASH Dietary Pattern and a Lower Risk of Incident Gout - The Nurses' Health Study

In our recent NIH-funded project to investigate several cardiovascular-metabolic dietary approaches for the outcome of incident gout (the clinical end-point of hyperuricemia), the DASH diet was associated with a lower risk of gout, whereas the Western dietary pattern was associated with an increased risk of gout, which would explain the rising prevalence of gout.⁸

In our extended analyses (N = 3,075 incident cases of gout), the top quintile most reflective of the DASH diet was found to be associated with a 32% lower risk for incident gout compared to the bottom quintile least reflective of the DASH diet. In contrast, the Western dietary pattern score was associated with an increased risk for gout. These observational data with the clinical endpoint of gout further support the DASH diet as an attractive dietary approach for gout.⁸

4. OVERVIEW OF DESIGN

This study will be an individual level, crossover RCT with 2 periods (**Figure**). The participants will be 40 adults with gout and hyperuricemia (≥ 18 years) who have SUA ≥ 7 mg/dL, who are not currently taking ULD. After informed consent, screening, and run-in, participants will be randomly assigned to each of two groups in random order: 1) Self-Directed (SD) vs. 2) DietitianDirected DASH Tailored (DD) with the provision of food. The primary outcome variable is SUA.

The duration of the intervention will be 4 weeks. Two screening visits will be used to determine interest and eligibility. The rationale for this timeline is that it is of sufficient duration to allow a complete effect of the intervention on uric acid to occur. Because it is not a prolonged period of intervention, the risk of non-compliance will be reduced, allowing for a better determination of the efficacy of the intervention. The DASH diet effects on SUA occur within 4 weeks and on blood pressure occur within 2 weeks, and are sustained from 2 weeks forward. As such, the 4 weeks will also provide sufficient time to see maximum diet effects on SUA and blood pressure and reduce the time period where recidivism is likely to occur.

Protocol visits for in-person data collection will occur during the screening period, at randomization, at week 4 after follow-up period 1 and follow-up period 2. At all protocol visits, our blinded data collectors will collect blood pressure and study questionnaires from participants in both arms of the study. Blood collection will be performed by phlebotomists blinded to the intervention arm.

5. STUDY POPULATION AND ELIGIBILITY

Eligibility criteria are summarized below. This trial focuses on gout in the setting of no active ULD use. Given potential potassium overloading from the DASH diet, we will exclude patients with hyperkalemia or CKD stage 4 or higher, similar to previous DASH trials, although the DASH diet is even expected to slow the progression of CKD.

Inclusion criteria:

- Age 18-100 years
- Self-reported gout diagnosis
- Serum Uric Acid ≥ 7 mg/dL

Exclusion criteria:

- Unstable or Stable ULD use or plans to initiate ULD
- Patients with hyperkalemia (>5 mmol/L)
- Consumption of more than 14 alcoholic drinks per week or more than 6 alcoholic drinks in one occasion
- Chronic kidney disease (GFR < 30 cc/min), active dialysis, or history of kidney transplant
- Inability to give informed consent
- Chronic steroid use, warfarin use, insulin use
- Unstable lipid, diabetes, and hypertension medication use (2 month period)
- Active heart attack, heart failure, angina, coronary bypass, COPD
- Active cancer or cancer treatment
- Active inflammatory bowel disease, malabsorption, history of major gastrointestinal surgery involving bowel resection
- Pregnant, plan to become pregnant, or breast feeding
- Plans to leave geographic area in the next 3 months
- Active participation in another clinical trial
- Significant food allergies, preferences, or intolerances
- Unable to give informed consent
- Unable to pick up foods at the research clinic during the DASH intervention phase
- Unable to transport or store food properly, lack of a cooking facility at home Terminal or mental illness

6. RECRUITMENT

Field centers

The trial will be conducted at a well-established field center in Central Maryland, namely, the ProHealth clinical research unit in West Baltimore, Maryland.

The ProHealth Clinical Research Unit is a dedicated research facility that has been the site for numerous NIH-sponsored trials. This participant-friendly clinical research facility is 15,000 ft² located in the Woodlawn suburb of Baltimore and is convenient to participants from Baltimore City, Baltimore County, Anne Arundel County, and Howard County. ProHealth has 9 exam rooms and 2 phlebotomy stations and space for up to 50 staff.

Recruitment strategies

We will implement a variety of strategies to achieve our recruitment target, i.e. ~40 participants. Our experience is that multiple strategies work synergistically to promote study name-brand recognition to enhance recruitment. We will employ the following approaches:

- (1) EPIC patient portal messages to patients of Johns Hopkins Hospital with an active patient portal. The Johns Hopkins University Core for Clinical Research Data Acquisition will develop a dynamic query of Hopkins patient's with a gout ICD-9 or ICD-10 code, age>18 years, and in zip codes surrounding the ProHealth Clinical Research Center. Those with an active patient portal will receive a portal message with a link to our website and other contact information. Those with an inactive patient portal will receive a mail invitational letter.
- (2) Community-based recruitment will be performed using a mailed brochure with a stamped, self-addressed reply card. Addresses will be purchased from local vendors.
- (3) Periodical advertisements: We will place a banner ad in local newspapers surrounding our clinical research center.
- (4) Billboards, radio, and bus advertisements will be considered targeting our immediate geography.
- (5) Facebook advertisements (including Instagram): These will target users with an interest in gout in the region surrounding our clinical research center. Advertisements will direct interested adults to our trial website.
- (6) Clinic contact: Study brochures will be placed in the rheumatology clinic waiting areas.

Recruitment of women and minorities

Given the demographic characteristics of individuals residing in central Maryland with gout, we anticipate that ~80% of participants will be men and ~40% will be African-American.

7. DATA COLLECTION AND MEASUREMENTS

Data collection contact schedule

Eligibility, baseline, and follow-up data will be collected by phone, through mailings, and at in-person visits. In-person data collection visits will primarily be conducted at the ProHealth Clinical Research Unit in Woodlawn, MD. In general, we try to be as flexible as possible to meet the needs of our participants. For example, we might divide or bundle data collection across visits. See Table below for an overview of proposed data collection items by visit. Some items might be dropped based upon participant burden, scientific considerations, available resources, and the results of field testing. The primary data collection points for participant-level data are as follows:

Pre-Screen Contact (PS) – A brief questionnaire will be administered by phone to identify potentially eligible participants quickly and efficiently.

Screening Visit 1 (SV1) – This in-person visit will include written informed consent for screening, questions about medical history, medications, and eligibility; serum collection for uric acid screening and urine specimen collection.

Screening Visit 2 (SV2) – This in-person visit will include further questions about demographic characteristics, baseline diet, physical activity, gout, and global pain. We will also measure height and weight and perform seated and standing blood pressure assessments (BP and OH), and a “Timed Up and Go” (TUG) test.

Randomization Visit (RZ) – This in-person visit will include additional questionnaires on physical activity, a repeat weight assessment, measurement of BP and OH. Participants will be provided an opaque envelop to learn the intervention sequence. They will subsequently be provided instructions on the next phase of the study.

Feeding Period 1 Visit (FP1) – This in-person visit includes diet screening, a medication questionnaire, physical activity questionnaires, pain assessments, and questions about adverse effects from diet, compliance, and palatability. In addition, we will perform phlebotomy, urine assessments, and physical examinations including weight, BP, OH, and the TUG test. Participants will also receive instructions for their next feeding assignment.

Feeding Period 2 Visit (FP2) – This in-person visit includes diet screening, a medication questionnaire, a physical activity questionnaire, a pain assessment, a questionnaire about adverse effects from diet, compliance, and palatability. In addition, we will perform phlebotomy, urine assessments, and physical examinations including weight, BP, OH, and the TUG test. We will also provide participants with some close-out materials including a certificate of appreciation.

Table. Data Collection Schedule

	Pre-	Screening/Baseline/Randomization			Feeding Periods Period	
	screen PSV	SV1	SV2	RZ	FP1	FP2/Close-out
Pre-screen questionnaire	✓					
Study description/instructions	✓	✓		✓		
Informed consent		✓				
Randomization assignment				✓		
Eligibility checklist		✓	✓			
Medication list questionnaire		✓	✓	✓	✓	✓
Medical history		✓				
Demographic questionnaire			✓			
Physical activity questionnaire (for Calorie estimator)			✓	✓	✓	✓
Gout questionnaire			✓			
Global pain and function questionnaire			✓		✓	✓
Diet compliance					✓	✓
Diet palatability/Symptom/diet tolerance questionnaire (DD intervention only)					✓	✓
Interim event			✓	✓	✓	✓
Diet screener (fruit/vegetables/fat)			✓		✓	✓
Serum collection		✓			✓	✓
Urine collection		✓			✓	✓
Seated blood pressure			✓	✓	✓	✓
Orthostatic hypotension			✓	✓	✓	✓
Height			✓			
Weight			✓	✓	✓	✓

TUG test			✓		✓	✓
Close-out survey with certificate						✓

Note: During the DASH intervention, participants will complete weekly food ordering calls with the study dietitian. Grocery orders will be documented.

Measurements

Primary outcome variable.

Uric acid. Fasting blood will be collected during SV1, FP1, and FP2 for SUA, blood glucose, total cholesterol (TC), HDL cholesterol (HDL-C), and triglycerides. LDL-C will be estimated by the equation (LDL=TC-HDL-triglyceride/5).

Clinical Blood Pressure. Clinical blood pressure (BP) will be determined by the OMRON 907XL. This device records BP using an oscillometric technique. The OMRON device has been validated against the mercury random zero. BP is obtained by trained and certified data collectors according to a standard protocol, adapted from the protocol used in the Omni-Heart trial. Three measurements (each separated by 30 seconds) are obtained at each visit on the right arm of participants after they rest quietly in the seated position for at least 5 minutes. A cuff of appropriate size is identified at the initial visit and used thereafter at all subsequent visits. Heart rate is also recorded by the OMRON device. We will repeat this assessment immediately after standing to assess BP regulation (orthostatic hypotension). BP will be measured at SV2, RZ, and both FPs. The average BP of SV2 and RZ will be used to estimate baseline BP. The average BPs measured after each 4-week period will be used to determine intervention effects on BP.

Secondary outcome variables.

- a. Urinary sodium and potassium and creatinine excretion. Spot urine collections, urinary sodium (Na), potassium (K), and creatinine excretion will be used to estimate group compliance with dietary aspects of the intervention (i.e., sodium excretion for salt intake and potassium excretion for fruit and vegetable intake). We will also measure urine pH and uric acid to explore the effects of the diets on urine excretion of uric acid as a potential mechanism for serum urate reduction.
- b. Other serum measures. While no specimens will be banked, we will measure serum sodium, potassium, chloride, bicarbonate, and transaminase levels as part of an extended metabolic panel used to determine uric acid levels.
- c. Questionnaires. The trial will collect questionnaire data from participants. These data will be used for a variety of purposes—baseline data to describe participants, outcome data to assess the effects of the trial interventions, and mediating variables to assess potential causal pathways. The Demographic Questionnaire is a self-reported assessment of basic patient characteristics. It assesses ethnicity, tobacco use, alcohol use, health insurance status, income, employment, marital status, and education level. The Medical History Questionnaire and Prescreening Questionnaire includes details related to gout history, kidney disease, diabetes, hypertension, cardiovascular disease, gastrointestinal conditions, cancer, pregnancy, and menopause. The Medication Use Questionnaire will be collected at baseline and during follow-up. The Fat/Fruit/Vegetable Screener, developed by the National Cancer Institute is a brief self-reported assessment of percent energy intake from fat, fruit, and vegetables. It queries respondents regarding consumption of a variety of food products that are high in fat over the past month. The Gout Assessment Form asks detailed question about gout history. The Pain Assessment Form asks about pain performing common tasks. Both the Gout Assessment Form and the Pain Assessment form use elements from other commonly used scales including the GAQ2.0, the SF36, and the WOMAC pain survey on global joint pain.⁹⁻

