8. QUALITY ASSURANCE AND QUALITY CONTROL

The investigative team understands the critical importance of collecting complete, high-quality data and developing procedures to accomplish this important objective. Core activities include:

- Standardization - maintaining common study documents (protocol, MOP, case report forms) with special efforts to minimize version control issues.
- Training – developing training procedures led by experienced investigators and senior staff, developing and implementing certification procedures and performance metrics, and conducting annual training.
- Robust data systems – implementing a web-based data entry system with duplicate data entry; using off-site data storage with automated back-up systems; programming data queries to check logic and consistency of data between forms over time; implementing replicate programming for major papers.
- Site visits – conducting site visits has an important role in promoting best practices, identifying operational problems not evident in trial reports, and maintaining a culture that promotes high quality.
- Performance monitoring with feedback – tracking enrollment and follow-up (observed/expected, overall and by key subgroups); monitoring missed visits, data completeness, protocol deviations, and data entry errors; distributing feedback through routine trial monitoring reports. These reports, together with constructive feedback, have an important role in identifying and resolving issues expeditiously.

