9. RANDOMIZATION AND MASKING

Randomization

A variable 2, 4, or 6 block randomization scheme will be generated the Johns Hopkins University Institute of Clinical and Translational Research. The scheme will entail two orders AB or BA consistent with our crossover design. Details of the block sizes will be concealed from study staff and investigators and generated prior to the study and placed in opaque, sealed envelopes. A designated staff member will open the envelope with the participant during the randomization visit after confirmation of eligibility and informed consent. This will be performed in a private location away from other staff. Once assigned order is revealed, this information will be shared with the study dietitian, who will provide instructions pertinent for each intervention phase. Order of intervention will not be shared with research technicians performing data assessments or with study investigators. Study personnel and investigators will not be unmasked until follow-up and all data collection are completed.

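### The 5 mmol/L potassium limit is applied only at screening; no rule compares the FP1 potassium with it, or passes it on, when SD-first participants move to DASH

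*Protocol*

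**What the plan says.** Protocol section 5 gives both the rule and its reason: "Given potential potassium overloading from the DASH diet, we will exclude patients with hyperkalemia or CKD stage 4 or higher". The exclusion list sets the figure: "Patients with hyperkalemia (>5 mmol/L)". Section 11 repeats the reason and describes the excluded condition as hyperkalemia at baseline.

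In the section 7 schedule, the row "Eligibility checklist" is ticked at SV1 and SV2 only. Section 9 adds a confirmation of eligibility at the randomization visit, where no blood is drawn.

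On sampling, section 7 states: "Fasting blood will be collected during SV1, FP1, and FP2 for SUA". Under other serum measures it adds: "we will measure serum sodium, potassium, chloride, bicarbonate, and transaminase levels as part of an extended metabolic panel used to determine uric acid levels". So a potassium result should exist from FP1. At that visit, "Participants will also receive instructions for their next feeding assignment". SAP section 3.1 confirms that there is no washout.

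On who knows what, section 9 states: "Order of intervention will not be shared with research technicians performing data assessments or with study investigators". The dietitian is told the order and, under section 10, places the weekly food orders.

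Section 11 has a study physician review all labs, and a designated clinician review both eligibility criteria and laboratory reports. Critically abnormal values go to the participant at once. Mildly abnormal values go out by letter with advice to see the primary care provider. The adverse event text adds that the clinician acts as appropriate on abnormal values.

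**The concern.** The limit exists because of exposure to DASH, not because of enrolment as such. For the SD-first sequence the two are separated by a 4-week period. When DASH is due to start, the trial already holds a more recent potassium than the one on which the participant was admitted, yet no rule uses it.

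A change since screening is plausible. Section 5 excludes only GFR below 30, and the SAP plans a subgroup with eGFR below 60 (section 3.4, stratified analysis). The SAP also anticipates changes in antihypertensive medication after randomization (section 3.4, sensitivity analyses).

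At stake is that a participant whose current potassium would have barred entry, for a reason specific to DASH, could begin DASH without anyone making that comparison. This is a safety point. It does not bear on the validity of the primary analysis.

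**Working it through.** No figure in the plan needs reproducing. The check sets provisions side by side, with some simple counts.

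**1. How many start DASH after FP1.** Allocation is 1:1 (SAP 3.1), so 40 / 2 = 20. Block sizes are 2, 4 and 6 (protocol section 9). At n = 40 an unfinished last block can hold only 2 or 4 people. The most uneven splits are 2:0 and 3:1, an imbalance of 2, so the range is 19 to 21.

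**2. Age of the screening potassium when DASH starts.** SV1 to FP2 is 10–12 weeks (section 10), each period is 4 weeks (section 4), and there is no washout.
- SD-first: 10 − 4 = 6 to 12 − 4 = 8 weeks.
- DASH-first: 10 − 8 = 2 to 12 − 8 = 4 weeks.

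**3. What could link the FP1 potassium to the start of DASH.**

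| Element needed | What the documents give |
|---|---|
| A value | Yes: FP1 panel |
| A limit | 5 mmol/L in section 5, for entry; no potassium figure in section 11 |
| A comparison at FP1 | None: checklist at SV1 and SV2, confirmation at randomization |
| A time for review relative to the switch | None |
| A route to the person who orders food | None: the dietitian has no stated role in lab results |
| A stated hold on groceries | None: possible only at the clinician's discretion |

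For contrast, section 11 gives numeric blood pressure limits (above 180/110 and above 160/100 mm Hg) with follow-up within 7 days and 1 month. Potassium, named there as a reason for exclusion, has no such limit, and critical and mild abnormality are not defined.

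**4. Who holds both facts.** The clinician sees the potassium. The dietitian knows that DASH is next. Section 9 withholds the order from investigators and keeps study personnel masked until data collection ends, so the clinician is probably masked, though the text does not name that role. No one is shown to hold both facts.

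**5. Timing.** Section 13 describes laboratory data as sent to the clinic by outside facilities. Neither turnaround nor the date of the first period-2 pick-up is stated, so the result may or may not arrive before the first food. Food is released weekly, about 4 times in the period, so a late result can still stop DASH at a later pick-up. No further blood is scheduled until FP2.

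**6. Size.** If p is the proportion of SD-first participants above 5 mmol/L at FP1, the expected number is 20 × p. The documents give no p. One expected participant would need p = 1/20, or 5%.

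**The case against.** The strongest reply is that 5 mmol/L is an entry criterion and no text promises to apply it again. That is right: the protocol does not contradict itself, and a reader should not infer that it does.

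The general controls are also real. A physician reviews every lab result, action on abnormal values is not confined to a letter, and there is 24/7 medical cover. Medication and interim-event forms are completed at FP1 and reviewed. Unstable hypertension medication and GFR below 30 are excluded at entry. The letter pathway is introduced in a passage about findings unrelated to the study, so a diet-related potassium might be handled differently. Participants know their own sequence, and a masked clinician can still advise delay.

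Three stronger readings are tempting, and none is supported:
- *That nobody looks at the FP1 potassium.* It is in the panel and all labs are reviewed.
- *That a high value would go unaddressed for 4 weeks of DASH.* Weekly release allows DASH to be stopped once the result is seen.
- *That the SD-first sequence is monitored less than the other.* It has one more potassium before DASH, and DASH-first participants also go 4 weeks on DASH without scheduled blood.

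Finally, section 8 refers to "maintaining common study documents (protocol, MOP, case report forms". The manual of procedures was not available and may contain a lab-alert step.

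What stands is narrower. For a value modestly above 5 mmol/L, these controls rest on discretion, with no limit, no route to the dietitian and a reviewer who probably does not know that DASH is next.

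**Conclusion.** The point holds in a limited form. The protocol's DASH-specific potassium limit is not applied to the one new potassium available before about 20 of 40 participants (19 to 21) start DASH, and neither document sends that value to the person who could hold the food. A markedly high value would probably be caught by general review, so the exposure is mainly values modestly above the limit.

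The figure of 20 is the size of one sequence, not an estimate of harm. The number actually above 5 mmol/L at FP1 is unknown and probably very small.

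The conclusion assumes that potassium is reported from the FP1 panel, that the reviewing clinician falls under the masking in section 9, and that the manual of procedures does not already contain this step. It is a safety gap of minor priority.

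**What to change.** In section 11, state that the study clinician compares every participant's FP1 potassium with the existing 5 mmol/L limit as soon as it is reported, whatever the sequence, and sends any value above it to the unmasked dietitian. If DASH is next or under way, the dietitian withholds the first or next DASH order until the clinician clears the participant, with a repeat potassium at the clinician's discretion. Because the check covers both sequences, the flag does not reveal order. FP2 stays on schedule where possible, and the participant remains in the intent-to-treat set.

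A compulsory wait for the result before the first period-2 pick-up is not needed. Only SD-first participants would wait, and a later FP2 could hint at sequence to masked staff.

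The cost is a short amendment that reuses an existing sample, limit, reviewer and dietitian contact. The downsides are an occasional repeat draw, a rare delayed or missed DASH week, and a rare off-diet uric acid value in the DASH period. If the manual already has such a step, a cross-reference in section 11 is enough.
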